5.2 Randomized Population

The Randomized population is defined as all subjects who are randomized to a treatment group.

5.3 Safety Population

The Safety population consists of all randomized subjects who received at least one intralesional dose of study medication.

February 27, 2018

The Safety population will be used in all safety/tolerability analyses unless otherwise stated. Subjects will be analyzed according to the dose they received.

5.4 Modified Intent-to-Treat (mITT)

The mITT population consists of all subjects in the Safety population who had at least one post-baseline measurement of the primary wart(s).

The mITT population will be used for analyses all efficacy endpoints including exploratory efficacy endpoints.

6 STUDY SUBJECTS

6.1 Subject Disposition

Subject disposition information, including the number and percent of subjects who completed treatment, discontinued treatment further broken down by primary reason for treatment discontinuation, subjects who completed the study and terminated early from the study further broken down by reason for early termination will be summarized by cohort and treatment for the Randomized population.

Subjects who completed treatment will be defined as those who completed all 10 injections, or with all injectable warts resolved by Efficacy Evaluation Visit (Visit 13). An injectable wart is defined as any measured wart.

Subjects who completed the study will be defined as those who completed treatment and both follow-up visits (Visit 14 and Visit 15).

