Nielsen- CFW-2D Page 26 of 54 Protocol Final version 5.0: 06Dec2016 response the second largest injectable common wart of all anatomical regions will be injected with CANDIN at the same dose. If the second largest common wart exhibits a complete response the third largest wart of all anatomical regions will be injected. If an injected wart recurs after exhibiting a complete response, it will be re-injected instead of the non-primary injected wart that was injected at the previous visit. This injection strategy will be repeated for a maximum of 10 injections per subject or until all injectable common warts exhibit a complete response, if it occurs before all 10 injections are used.

3. Cohort 3: If the safety data of the 2nd cohort support continuation of the study (defined as medical assessment of the first eight (8) subjects (of cohort 2) completing three (3) injections), the approximately 52 subjects of cohort 3 will receive either 0.3 mL/wart CANDIN (n=39) or placebo (n=13) (total per visit ≤ 1.2 mL). Subjects in cohort 3 must have injectable common warts in at least 2 different anatomic regions. CANDIN or placebo will be injected under the largest wart (primary) per major anatomical region (left or right; arm, hand, leg, foot (excluding sole) or the torso) for a minimum of two (2) and a maximum of four (4) injections per visit every second week (14 +/- 2 days) for a maximum of 10 visits with injections. No more than one wart per anatomical region will be injected on any given visit. If any primary injected wart exhibits a complete response, the next largest injectable common wart will be injected with CANDIN at the same dose (maximum of 4 injections per visit) providing the new injectable wart is not within the same anatomical region as other currently injected warts. If an injected wart recurs after exhibiting a complete response, it will be re-injected instead of the non-primary injected wart that was injected at the previous visit. This injection strategy will be repeated for a maximum total of 10 injection visits per subject or until all injectable common warts exhibit a complete response, if it occurs before the end of the 10 injection visits.

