2.3 Exploratory Objectives

3 STUDY OVERVIEW

3.1 Study Design

This is a placebo-controlled, double-blind (subject, Investigator, and site staff with the exception of unblinded dedicated staff to handle study medication), multi-center, Phase IIa study with 3 dose cohorts, randomized to Candin or placebo in a 3:1 ratio. The main study will be up to 20 weeks (10 doses administered every other week) or until a subject has complete resolution of all injected common warts. Subjects who cannot tolerate dosing every 2 weeks (14 ± 2 days) due to a local tolerance issue may be injected at 3-week (21 ± 2 days) intervals for up to 10 doses, increasing the length of the study to 29 weeks. Subjects will be followed for 4 months after final injection(s) for evidence of new or reoccurring warts and for safety evaluation.

Approximately 156 (male or female) subjects aged 18 to 65 inclusive at the date of consent, with 3 to 20 common warts on hands, feet (excluding soles), limbs, and/or trunk will be included in this study. It is assumed that approximately 80% of the subjects will either complete the study or reach complete resolution. Drop-outs will not be replaced. Refer to Section 9 for sample size and power of the study.

Subjects will be included in three cohorts as follows:

Cohort 1: Approximately fifty-two subjects will receive 0.3 mL of either Candin (n=39) or placebo (n=13) intralesionally in the largest (primary) common wart every second week (14 ± 2 days) for a maximum of 10 injections. If the primary common wart exhibits a complete response, the second largest injectable common wart of all anatomical regions will be injected with the randomized study medication at the same dose. If the second largest common wart exhibits a complete response, the third largest wart of all anatomical regions will be injected. If an injected wart recurs after exhibiting a complete response, it will be re-injected instead of the non-primary injected wart that was injected at the previous visit. This injection strategy will be repeated for a maximum of 10 injections per subject, or until all injectable

common warts exhibits a complete response if that occurs before all 10 injections are used.

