Cohort 2: Approximately fifty-two subjects will receive 0.5 mL of either Candin (n=39) or placebo (n=13) intralesionally in the largest (primary) common wart every second week $(14 \pm 2 \text{ days})$ for a maximum of 10 injections. The same procedures will be followed in the event of complete response or recurrence as described for Cohort 1.

Cohort 3: If the safety data from Cohort 2 support continuation of the study (defined as medical assessment of the first eight subjects of Cohort 2 completing three injections), approximately 52 subjects planned for Cohort 3 will receive either 0.3 mL/wart Candin (n=39) or placebo (n=13), with a total per visit not to exceed 1.2 mL. Subjects in Cohort 3 must have injectable common warts in at least 2 different anatomic regions. Candin or placebo will be injected under the largest (primary) wart per major anatomical region (left or right; arm, hand, leg, foot excluding sole, or the torso) for a minimum of two and a maximum of four injections per visit, every second week (14 ± 2 days) for a maximum of 10 visits with injections. No more than one wart per anatomical region will be injected on any given visit. If any primary injected wart exhibits a complete response, the next largest injectable common wart will be injected with the randomized study medication at the same dose (maximum of 4 injections per visit), providing the new injectable wart is not within the same anatomical region as other currently injected warts. (If an injected wart recurs after exhibiting a complete response, it will be reinjected instead of the non-primary injected wart that was injected at the previous visit.) This injection strategy will be repeated for a maximum total of 10 injection visits per subject or until all injectable common warts exhibit a complete response, if it occurs before the end of the 10 injection visits.

Two Follow-up visits are included in the study to further assess the efficacy and safety of the study medication. Follow-up information will be obtained for subjects who discontinue their participation in the study. All procedures scheduled for during Follow-up Visit 1 and Follow-up Visit 2 should be completed for early termination subjects, as well as for those subjects who have complete resolution of all common warts prior to their Efficacy Evaluation visit (V13).

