6.5 Extent of Exposure

The extent of exposure to randomized study medication will be presented as a frequency table of the total number of injections administered over study assessment period.

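### SAP 6.1 defines treatment completion as 10 injections in every cohort, but a Cohort 3 course is up to 10 visits with 2 to 4 injections each, so the rule read literally is met at visit 3, 4 or 5

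*SAP*

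**What the plan says.** SAP 6.1 (Subject Disposition) reports treatment completion and discontinuation, and study completion and early termination, by cohort and treatment for the Randomized population. The completion rule is the same for all three cohorts: "Subjects who completed treatment will be defined as those who completed all 10 injections", or, alternatively, all injectable warts resolved by Visit 13. A study completer is a treatment completer who also attended Visits 14 and 15.

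SAP 3.1 (Study Design) describes two kinds of course. For Cohort 1, and by reference Cohort 2: "This injection strategy will be repeated for a maximum of 10 injections per subject". For Cohort 3, dosing is "for a minimum of two and a maximum of four injections per visit", with volume limited as follows: "with a total per visit not to exceed 1.2 mL". The upper limit on the Cohort 3 course is stated in visits, and Protocol 6.1 uses the same words: "This injection strategy will be repeated for a maximum total of 10 injection visits per subject".

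SAP 6.3 (Treatment Compliance) divides injections given by warts eligible for injection, so it counts per wart. SAP 6.5 (Extent of Exposure) is "presented as a frequency table of the total number of injections administered over study assessment period".

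The SAP text available gives no separate completion rule for Cohort 3.

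**The concern.** Ten injections marks the end of the course in Cohorts 1 and 2, but in Cohort 3 it can mark a point well before the end. A programmer who applies SAP 6.1 as written, with the per-wart unit used in SAP 3.1 and 6.3, would hold the cohorts to different standards. A Cohort 1 or 2 subject who misses one dosing visit fails the rule unless the warts have resolved. A Cohort 3 subject could miss several and pass.

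The misclassification can carry into study completion. SAP 3.1 asks that the procedures of both follow-up visits also be completed for subjects who terminate early. A Cohort 3 subject who stopped dosing early and attended Visits 14 and 15 could therefore be counted as completing both treatment and study.

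At stake is the by-cohort comparison of disposition. It would flatter the cohort with the largest permitted volume per visit, which has 52 of the 156 planned subjects.

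**Working it through.** **Inputs.** The completion threshold is 10 injections (SAP 6.1). Cohorts 1 and 2 receive 1 injection per visit and at most 10 injections (SAP 3.1). Cohort 3 receives k = 2, 3 or 4 injections of 0.3 mL per visit for at most 10 injection visits (SAP 3.1, Protocol 6.1).

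**Check on the unit.** The plan's own volume limit confirms that one injection means one wart: 4 × 0.3 mL = 1.2 mL per visit.

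**Visits needed to reach the threshold.** With a constant k per visit, the number of visits is 10/k rounded up. The maximum course is 10 × k injections.

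| Injections per visit | Visit at which 10 is reached | Injections by then | Maximum course | Share of course | Visits left |
|---|---|---|---|---|---|
| 1 (Cohorts 1, 2) | 10 | 10 | 10 | 100% | 0 |
| 2 | 5 | 10 | 20 | 50% | 5 |
| 3 | 4 | 12 | 30 | 40% | 6 |
| 4 | 3 | 12 | 40 | 30% | 7 |

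**Mixed patterns.** If the number varies between 2 and 4 from visit to visit, two visits give at most 8 injections and five visits give at least 10. Every such pattern therefore crosses the threshold at visit 3, 4 or 5.

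**Timing.** On the two-week schedule, visit v falls about 2 × (v − 1) weeks after Day 1. Visits 3, 4 and 5 fall at about weeks 4, 6 and 8, and the tenth injection visit at about week 18.

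**Who does not pass.** At two per visit, stopping after visit 3 or 4 gives 6 or 8 injections. At three per visit, stopping after visit 3 gives 9. None of these meets the rule. If warts resolve and fewer than two stay eligible, the threshold comes later. For example, assuming two visits at two injections and one per visit after that, 2 + 2 = 4 leaves 6 more visits, so ten is reached at visit 8.

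**Where the rule is used.** It defines treatment completion and, through it, study completion in SAP 6.1. The primary endpoint (SAP 4.1), the Safety and mITT populations (SAP 5.3, 5.4) and the TEAE summaries (SAP 7.3.1) make no reference to it.

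**The case against.** The best reply is that the authors meant the ten-dose schedule. The word *all* suggests a whole course, and Cohort 3 has no course of ten single-wart injections. At a constant three or four per visit the running count never equals ten. Protocol 6.1 opens by giving every subject, including those in Cohort 3 with more than one injection per visit, a limit of ten doses, so a dose there corresponds to a visit. SAP 3.1 and footnote 2 of SAP Table 1 also speak of ten doses, and the table marks intralesional injection at exactly ten visits, V3 to V12. On this reading SAP 6.1 already means ten visits.

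That reading is plausible, and it is why this is a point of wording and not a demonstrated error. It does not settle the matter, because SAP 6.1 says injections, not doses. SAP 3.1 uses injections and injection visits as different units within its Cohort 3 paragraph, and SAP 6.3 counts per wart.

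A reader might also infer more than the documents support:

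- *That every Cohort 3 subject who stops after three to five visits would count as a completer.* This is not so: the count depends on injections per visit, as shown above.
- *That withdrawals for poor tolerability would disappear.* SAP 7.3.1 tabulates TEAEs leading to withdrawal and injection site TEAEs separately, and SAP 4.4 assesses tolerability through adverse events, laboratory results and vital signs, not through completion rates. Stops for other reasons lack that second source.
- *That the exposure table in SAP 6.5 is wrong.* A count of 12 injections is a correct count. SAP 7.1 generally presents summaries by treatment group, so Cohort 3 would have its own column. Adding visits would make the table easier to read across cohorts, but it corrects no error.

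**Conclusion.** The completion rule in SAP 6.1 does not match the Cohort 3 course in SAP 3.1 and should be clarified. Read literally, it is met in Cohort 3 after 3 to 5 of 10 possible injection visits while two to four warts are injected each time, against all 10 visits in Cohorts 1 and 2 unless the warts resolve. Some early stoppers in Cohort 3 would then be reported as treatment completers and, with both follow-up visits, as study completers.

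This rests on reading injections in SAP 6.1 per wart, as in SAP 3.1 and 6.3. If ten injection visits was intended, only the wording is at fault. How many subjects would be misclassified cannot be worked out, because the documents give neither the distribution of injected warts per Cohort 3 subject nor the pattern of early stopping. The consequence is confined to descriptive disposition counts by cohort. Minor severity.

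**What to change.** In SAP 6.1, replace the ten-injection condition with completion of all 10 injection visits, which matches SAP 3.1, and leave the alternative of all injectable warts resolved by Visit 13 as it stands. Counting visits means the same thing in all three cohorts. This changes how subjects are classified in the tables and does not alter dosing.

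Optionally, add the number of injection visits to the exposure table in SAP 6.5.

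The cost is one phrase in the SAP and, if the literal rule has been programmed, a small change to the disposition derivation. Injections are given at scheduled visits, so no new data should be needed. The downside is that the reported Cohort 3 completion rate may be lower than under the literal rule.

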6.2 Demographic and Baseline Characteristics

Demographic and baseline characteristics will be summarized descriptively by cohort and treatment for the Safety, mITT, and Evaluable populations. The demographic characteristics include, but are not limited to: gender, age, age group (<45 years or ≥45 years), race, and ethnicity. Baseline characteristics include:

- body weight, height, and body mass index (BMI).
- number of common warts mapped.
- mean area of common warts initially mapped and measured.
- location of common warts by anatomical region (left arm, right arm, left hand, right hand, left leg, right leg, left foot excluding sole, right foot excluding sole, torso) and number of anatomical regions (single vs multiple).
- mean area of primary injected wart(s)
- age (weeks) of primary injected wart(s). For Cohort 3 subjects use the maximum age of the primary injected warts.

The medical histories of subjects will be provided in a data listing.

6.3 Treatment Compliance

Subjects are to receive injections every 2 weeks (or 3 weeks for those subjects who cannot tolerate dosing every 2 weeks due to a local tolerance issue). The Investigator will inject the entire volume of drug into a single wart (0.3 mL for Cohort 1; 0.5 mL for Cohort 2; and 0.3 mL per wart up to 1.2 mL total injected volume for Cohort 3). If the entire volume cannot be injected in a single injection, the Investigator will document that in the CRF and will divide

the randomized study medication between two or more injection sites around the same wart until the entire dose of randomized study medication has been injected, if possible. Treatment compliance data will be reviewed manually based on comments provided by the Investigator.

For each subject, the treatment compliance will be calculated by dividing the total number of injections administered by the sum of the total number of warts eligible for injection (as defined by study Protocol) at each injection visit multiplied by 100. The treatment compliance will be summarized descriptively by cohort and treatment for the Safety Population.

6.4 Protocol Deviations

Protocol deviations based on the inclusion/exclusion criteria at the time of enrollment will be summarized by cohort and treatment for the Randomized population. All protocol deviations occurring during the study period will also be summarized by cohort and treatment for the Safety Population. Subjects with any important protocol deviations that would affect efficacy will be identified and excluded from the Evaluable population. Important protocol deviations will be determined prior to treatment unblinding and database lock.

6.5 Extent of Exposure

The extent of exposure to randomized study medication will be presented as a frequency table of the total number of injections administered over study assessment period.

6.6 Concomitant Medications

All medications are to be coded using the current versions of WHO Drug Dictionary and Anatomical Therapeutic Chemical (ATC) classification system.

Medications will be classified as:

- Pre-treatment medications: medications taken and stopped prior to the first dose date.
- Concomitant medications: medications taken after receiving the first injection of the randomized study medication. These belong to the following categories:
 - O Prior concomitant medications: medications started prior to the first dose of randomized study medication and continuing past the first dose date.
 - New concomitant medications: medications started during or after the first dose date of the randomized study medication and prior to the first Follow-up visit (Visit 14).
 - New concomitant medications in Follow-up period: medications started during or after the first Follow-up visit (Visit 14) and prior to the second Follow-up visit (Visit 15).

Number and percent of the Safety subjects with each of the above-mentioned medications will be summarized by ATC classification (ATC level 2 and level 4).

7 STATISTICAL METHODS OF ANALYSIS

7.1 General Considerations

In general, all data summaries will be presented by treatment group; 'pooled placebo', 'Cohort 1: 0.3 mL Candin', 'Cohort 2: 0.5 mL Candin' and 'Cohort 3: 0.3 mL Candin'. When statistically comparing the effectiveness of the two Candin doses, 0.3 mL and 0.5 mL, with placebo, Cohort 3 subjects will be pooled with Cohort 1 subjects with common warts at baseline in multiple anatomical regions.

Continuous variables will be summarized by n, mean, standard deviation, median, minimum, and maximum. Categorical variables will be summarized by frequency and percent in corresponding categories.

A subject's age (years) will be calculated as of the date of informed consent as follows:

Age = Year of informed consent - Year of birth

-1 (if birth day and month are after day and month of informed consent)

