3.2 Secondary Endpoints

1. Incidence of site injection AE for all subjects and TEAE for subjects randomized to CANDIN

Protocol Final version 5.0: 06Dec2016

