6 TREATMENT

6.1 Treatment Administered

Subjects who fulfill all the inclusion and none of the exclusion criteria may be accepted in the study. Each subject should read and sign an informed consent form prior to any screening procedures being performed. This study involves a comparison of an intralesional injection of CANDIN with an intralesional injection of placebo (unpreserved normal saline solution) in common warts. Subjects will receive one (Cohorts 1 and 2) or more (Cohort 3) intralesional injections every two weeks (14 +/- 2 days) at the region of the interdigitated base of wart (epidermal/dermal junction) for up to 20 weeks (a maximum of 10 doses per subject) or up to resolution of all injectable warts. Subjects who experience local tolerance issues when dosing is performed at 2-week intervals may be injected at 3-week intervals (21 +/- 2 days) also for a maximum of 10 doses per subject.

Subjects will be included in three cohorts as follows:

- 1. Cohort 1: Approximately 52 subjects will receive 0.3 mL of either CANDIN (n=39) or placebo (n=13) intralesionally in the largest common wart (primary) every second week (14 +/- 2 days) for a maximum of 10 injections. If the primary common wart exhibits a complete response, the second largest injectable common wart of all anatomical regions will be injected with CANDIN at the same dose. If the second largest common wart exhibits a complete response, the third largest of all anatomical regions will be injected. If an injected wart recurs after exhibiting a complete response, it will be re-injected instead of the non-primary injected wart that was injected at the previous visit. This injection strategy will be repeated for a maximum of 10 injections per subject or until all injectable common warts exhibit a complete response, if it occurs before all 10 injections are used.
- 2. **Cohort 2:** Approximately 52 subjects will receive 0.5 mL of either CANDIN (n=39) or placebo (n=13) intralesionally in the largest common wart every second week (14 +/- 2 days) for a maximum of 10 injections. If the primary common wart exhibits a complete

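### Injection-site reactions: one pooled placebo column mixes single- and multi-injection subjects, which can overstate the excess over placebo in Cohort 3 and understate it in Cohorts 1 and 2

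*SAP*

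**What the plan says.** SAP 7.1 sets the default display: in general, "all data summaries will be presented by treatment group", where pooled placebo is the first of four columns and the three CANDIN cohorts are the others. SAP 7.3.1 says that injection-site TEAEs get a further summary but names no columns for it. Protocol 14.5.2.1 also reports TEAEs by treatment group, with injection-site events handled separately.

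The placebo subjects do not share one injection schedule. In Cohorts 1 and 2 (Protocol 6.1) a placebo subject has one wart injected per visit, with 0.3 mL or 0.5 mL. In Cohort 3, subjects receive "0.3 mL/wart Candin (n=39) or placebo (n=13), with a total per visit not to exceed 1.2 mL" (SAP 3.1), and both arms are injected "for a minimum of two (2) and a maximum of four (4) injections per visit" (Protocol 6.1; SAP 3.1 agrees). The maximum is 10 injection visits in every cohort.

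Protocol 3.2 names "Incidence of site injection AE for all subjects" as a secondary endpoint. SAP 6.5 tabulates the number of injections given, but no adverse-event rate uses that number as a denominator. Protocol 14.5 makes pooling depend on the three cohorts' placebo data looking comparable.

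**The concern.** Each needle is a further opportunity for a local reaction, and incidence counts a subject once. If saline reactions accumulate with needles, the Cohort 3 placebo subjects will show a higher incidence than those in Cohorts 1 and 2. A pooled column then sits between the two and matches neither by number of injections. Cohort 3 is set against a placebo column made up mostly of single-injection subjects, and Cohorts 1 and 2 against one containing some multi-injection subjects.

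At stake is how readers judge the local tolerability of the multi-wart regimen against the single-wart regimens. Randomisation to CANDIN or placebo within each cohort supplies a placebo group on the same injection schedule, and the pooled display sets that comparison aside.

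**Working it through.** **Inputs from the documents.** Placebo numbers: SAP Table 2 gives 8 + 5 = 13 in Cohort 1 and 8 + 5 = 13 in Cohort 2. The Cohort 3 row of that table is broken in the available text, so its 13 comes from Protocol 6.1 and SAP 3.1. The total is 39, and the single-injection share is 26/39 = 66.7%. Injections per visit: 1 in Cohorts 1 and 2, k = 2 to 4 in Cohort 3. Visits: at most 10.

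**Assumed inputs.** The documents give no saline reaction risk per injection, q. I use 1% to 30%, independent between injections, with 10 visits, constant k, and the same q in every placebo subject.

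**Size of the shift, whatever the model.** Let p1 and p3 be the placebo incidences with single and multiple injections.

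- Pooled = (26·p1 + 13·p3)/39 = (2/3)p1 + (1/3)p3.
- Cohort 3: p3 − pooled = (2/3)(p3 − p1). The excess over placebo is too large by this amount.
- Cohorts 1 and 2: pooled − p1 = (1/3)(p3 − p1). The excess over placebo is too small by this amount.

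**Under the assumptions.** p1 = 1 − (1 − q)^10 and p3 = 1 − (1 − q)^(10k). For q = 2% and k = 3: p1 = 1 − 0.98^10 = 18.3%, p3 = 1 − 0.98^30 = 45.5%, and pooled = (26 × 18.3 + 13 × 45.5)/39, about 27.3%. With no drug effect, Cohort 3 looks 18.1 points worse than placebo, and Cohorts 1 and 2 look 9.1 points better.

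The range, with k = 2 / k = 4 in each cell and shifts in percentage points:

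| q | p1 (%) | p3 (%) | Pooled (%) | Cohort 3 shift | Cohorts 1–2 shift |
|---|---|---|---|---|---|
| 1% | 9.6 | 18.2 / 33.1 | 12.4 / 17.4 | +5.8 / +15.7 | −2.9 / −7.8 |
| 2% | 18.3 | 33.2 / 55.4 | 23.3 / 30.7 | +10.0 / +24.8 | −5.0 / −12.4 |
| 5% | 40.1 | 64.2 / 87.1 | 48.1 / 55.8 | +16.0 / +31.3 | −8.0 / −15.7 |
| 10% | 65.1 | 87.8 / 98.5 | 72.7 / 76.3 | +15.1 / +22.3 | −7.6 / −11.1 |
| 20% | 89.3 | 98.8 / 100.0 | 92.5 / 92.8 | +6.4 / +7.1 | −3.2 / −3.6 |
| 30% | 97.2 | 99.9 / 100.0 | 98.1 / 98.1 | +1.8 / +1.9 | −0.9 / −0.9 |

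In subjects, at q = 5% and k = 2 with no drug effect, one expects 25.0 of 39 reacting in Cohort 3, 18.8 of 39 in pooled placebo and 15.6 of 39 in each of Cohorts 1 and 2.

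**Limits of the model.** Writing u = 1 − p1, the gap is u − u^k. At k = 4 the largest possible shifts are +31.5 and −15.7 points. The function is concave in u, so for a given p1 any variation in risk between subjects makes the gap smaller. With q rather than p1 held fixed, clustering also lowers p1, so at 20–30% it need not shrink the gap. Fewer visits change each row: at one visit the Cohort 3 shift is 0.7 to 2.0 points at q = 1%, 3.2 to 9.0 at 5%, and 10.7 to 26.0 at 20%.

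**Event counts.** SAP 7.3.1 also plans these. Mean injections per pooled placebo visit are (26 + 13k)/39 = (2 + k)/3. With equal risk per injection, equal visits and every reacting wart counted, expected events relative to pooled placebo are 3k/(2 + k) = 1.5 to 2.0 in Cohort 3, and 3/(2 + k) = 0.75 to 0.50 in Cohorts 1 and 2, for k = 2 to 4. These ratios need neither a value of q nor independence.

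**The case against.** A reader might infer that pooling inflates the reactions reported for Cohort 3 or hides those in Cohorts 1 and 2. The documents do not support that: each CANDIN cohort has its own column and its incidence is shown in full. Only the informal difference from placebo moves. No test of adverse-event rates is described, and SAP 7.1.1 calls the study exploratory.

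A reader might also infer that the plan pools regardless of the data. Protocol 14.5 requires a comparability check first, and a gap such as 18% against 45% is what that check should catch. This counts in the plan's favour, but it is a weak safeguard. It has no criterion, does not say whether safety data are examined, and rests on 13 subjects per cohort. The condition is not in the visible SAP text. Parts of the SAP are not visible, so one cannot say that it was dropped.

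Three further points stand:

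- The pooled column for injection-site TEAEs is an inference from SAP 7.1, which speaks only in general. SAP 6.1 to 6.4 do summarise by cohort and treatment, but SAP 7.3.1 does not say so.
- Event counts and an injection-exposure table are already planned, so most ingredients of a per-injection rate exist. What is missing is the ratio and the split.
- The mismatch is clear for needle count, less so for volume. Mean pooled saline volume per visit is between (0.3 + 0.5 + 0.6)/3 = 0.47 mL and (0.3 + 0.5 + 1.2)/3 = 0.67 mL. For a volume-driven reaction, Cohort 2 at 0.5 mL is therefore roughly matched at the low end.

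**Conclusion.** The point holds as a flaw in a descriptive comparison on a named secondary endpoint. Followed as visible, the plan gives no CANDIN cohort a placebo column with the same number of injections per visit. The direction of the distortion depends on saline reactions per subject rising with the number of injections, and its split of two thirds to one third follows from the allocation. Its size cannot be fixed from the documents: it could be large (up to about 31 points for Cohort 3 and 16 for Cohorts 1 and 2) or negligible, and it vanishes if placebo incidence does not differ by cohort. This is a reporting correction that should be made before the tables are produced. It does not show that the safety data would be wrong or concealed.

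**What to change.** In SAP 7.3.1, for injection-site TEAEs:

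- Keep the pooled placebo column and add two more: single-injection placebo (Cohorts 1 and 2, n=26) and multi-injection placebo (Cohort 3, n=13).
- Report events per 100 injections for every group, using the injection counts from SAP 6.5. State whether reactions at several warts on one visit count as one event or several; the visible text does not say.
- Use pooled placebo alone for all other TEAEs.

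The cost is one extra descriptive table from data already collected, with no change to study conduct. The price is precision. With zero events, the one-sided 95% upper limit, 1 − 0.05^(1/n), is 20.6% for n=13 and 10.9% for n=26, against 7.4% for n=39. At q = 5% and k = 2, the standard error of the Cohort 3 difference rises from 11.1 to 15.4 points. The single-injection column still mixes 0.3 mL and 0.5 mL of saline, which a footnote should say.
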